7. PLANNED ANALYSIS

Descriptive statistics for continuous variables will generally be N (number of patients with non-missing values), arithmetic mean, standard deviation (SD), minimum, Q1 (lower quartile), median, Q3 (upper quartile) and maximum. In general, means, medians, other quartiles and SDs will be presented to one more decimal place than the raw data. Minimums and maximums will be presented to the same number of decimal places as the raw data.

For BI 456906 plasma concentrations, CV (arithmetic coefficient of variation), gMean (geometric mean) and gCV (geometric coefficient of variation) will also be presented. The data format for descriptive statistics of concentrations will be identical with the data format of the respective concentrations.

Tabulations of frequencies for categorical data will include all possible non-missing categories unless otherwise specified (e.g. AE terms), and will display the number of patients in a category as well as the percentage (%) relative to the respective treatment group. Percentages will be rounded to one decimal place. A missing category will be displayed only if there are actually missing values. Percentages will be based on all patients in the respective patient set whether they have non-missing values or not.

Disposition

The disposition of patients will be displayed. This table will present the number of patients enrolled, randomised and treated. The number treated will be further presented separating the dose escalation and maintenance periods. Planned maintenance treatment (see [Section 6.1.2](#)) will be used for this table.

The number of patients who completed or who prematurely discontinued study treatment will be summarised, along with the categorization of the primary reason for treatment discontinuation. The number of patients and reasons for prematurely discontinuing treatment will also be displayed separately for the dose escalation and maintenance periods.

The number of patients who completed or who prematurely withdrew from the study will be summarised, along with the categorization of the primary reason for study withdrawal.

Where shown on the disposition table, the percentages will be of the number of patients treated in each treatment group.

Kaplan-Meier estimates will be presented graphically by treatment group for time to early treatment discontinuation (defined as *treatment discontinuation date – treatment start date + 1*). In this analysis, patients who did not discontinue treatment early will be censored using the date on which they completed treatment.

The frequency of patients in each of the different analysis sets ([Section 6.3](#)) will also be tabulated by treatment. This will be done for both planned and actual maintenance treatment.

IPDs will be summarised and listed for the randomised set using planned maintenance treatment.

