4.1.4 Drug assignment and administration of doses for each patient

Table 4.1.4:1 Dose Escalation Scheme

| Dose group | Weekly dose in (mg) | | | | | | | | | | | | | | | | | | | |
|-------------------|---|---|-----|---|-----------------|---|-----------------|---|-----------------|----|--|----|-----------------|----|-----------------|----|-----------------|----|-----------------|----|
| | Fixed escalation (titration is not allowed) | | | | | | | | | | Flexible escalation (titration is allowed) | | | | | | | | | |
| Week of treatment | 1 | 2 | 3 | 4 | 5 | 6 | 7 | 8 | 9 | 10 | 11 | 12 | 13 | 14 | 15 | 16 | 17 | 18 | 19 | 20 |
| Escalation | | | 1st | | 2 nd | | 3 rd | | 4 th | | 5 th | | 6 th | | 7 th | | 8 th | | 9 th | |
| BI A | 0.3 | | 0.6 | | 0.6 | | 0.6 | | 0.6 | | 0.6 | | 0.6 | | 0.6 | | 0.6 | | 0.6 | |
| BI B | 0.3 | | 0.6 | | 0.9 | | 1.2 | | 1.2 | | 1.8 | | 1.8 | | 2.4 | | 2.4 | | 2.4 | |
| BI C | 0.3 | | 0.6 | | 0.9 | | 1.2 | | 1.2 | | 1.8 | | 2.4 | | 3.0 | | 3.6 | | 3.6 | |
| BI D | 0.3 | | 0.6 | | 0.9 | | 1.2 | | 1.8 | | 2.4 | | 3.3 | | 4.2 | | 4.8 | | 4.8 | |

Fixed dose escalation phase (week 1- week 10)

During this phase the patient will receive planned dose as described Table 4.1.4:1 and titration within the dose group will not be allowed. Patients who cannot tolerate study drug during this period despite of all the efforts taken, will be discontinued from treatment.

Tolerability assessment after 10 weeks

Tolerability will be assessed after 10 weeks of treatment prior to dosing (visit 7). Patients who cannot tolerate medication in the week after dosing of week 10, will not continue titration to the next step, but will be moved to the next lower dosing available at week 11 and continue with this new scheme for the remaining visits

- Patients of Group D will then follow scheme of group C
- Patients of Group C and B will then follow scheme of group A
- For patients of group A, there is no lower dose possible. They will be maintained with same scheme, and if they again cannot tolerate at next visit they will be discontinued

Flexible dose escalation phase (week 11- week 20)

During this time, the investigator should make every effort to follow every two weeks dose escalation however, adjusting dosing scheme based on the patient tolerability of GI AEs will be allowed, in a blinded manner, as per the below:

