6.1.3 Actual Maintenance Treatment

According to the rules for escalating and adjusting the BI 456906 dose given in the CTP, it is envisaged that some patients may not receive the planned maintenance treatment according to the randomised treatment group, whilst nevertheless remaining on treatment.

Actual maintenance treatment will therefore be defined for analysis as follows:

- If the actual dose at the start of the maintenance period is known to be less than the planned maintenance dose to which the patient was randomised, then actual maintenance treatment will be defined as this dose at the start of the maintenance period (which is expected to be one of the lower planned maintenance doses).
- If the patient was known to have discontinued treatment during the dose escalation period, actual maintenance treatment will be defined as the next planned maintenance dose up from the last dose which was taken prior to the dose at the time of discontinuation. This is specified in the table below, for all dosing possibilities planned in the CTP. The same rule will be applied irrespective of the reason for discontinuing treatment during the dose escalation period.

Table 6.1.3: 1 Definition of actual maintenance treatment for patients randomised to active BI 456906 maintenance treatment who discontinued treatment during the dose escalation period

Dose at discontinuation / Previous dose	Actual maintenance treatment
0.3 mg / NA	0.6 mg
0.6 mg / 0.3 mg	0.6 mg
0.9 mg / 0.6 mg	2.4 mg
1.2 mg / 0.9 mg	2.4 mg
1.8 mg / 1.2 mg	2.4 mg
2.4 mg / 1.8 mg	2.4 mg
3.0 mg / 2.4 mg	3.6 mg
3.3 mg / 2.4 mg	3.6 mg
3.6 mg / 3.0 mg	3.6 mg
4.2 mg / 3.3 mg	3.6 mg
4.8 mg / 4.2 mg	4.8 mg

- In all other cases, actual maintenance treatment will be defined equal to planned maintenance treatment.
- All patients randomised to placebo maintenance treatment will be assigned to placebo for actual maintenance treatment.

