6.3 SUBJECT SETS ANALYSED

The following analysis sets will be defined:

Screened Set

The screened set (SS) includes all patients for whom a signed informed consent is available at the time of final DBL. It will be used only for display of patient disposition.

Randomised Set

The randomised set (RS) includes all screened patients who were randomised in the trial, regardless of whether any study drug was taken. It will be used only for display of patient disposition and IPDs.

Treatment assignment will be as randomised (i.e. planned maintenance treatment).

Treated Set

The treated set (TS) is defined as all randomised patients who received at least one dose of study treatment.

The TS will be used for presentation of demographic/baseline data, concomitant medications/diagnoses, treatment exposure and safety.

Treatment assignment will be according to actual maintenance treatment (see [Section 6.1.3](#)), but certain AE summaries will also consider assignment according to planned (i.e. randomised) maintenance treatment.

It is not expected on the database that the situation in which a patient could be treated without randomisation will exist. Documentation is in place by the Interactive Response Technology (IRT) vendor, which states that, should any patient be given treatment at the site in error without randomisation, such a patient will be subsequently randomised to a treatment which is not incompatible with the one given in error.

Full Analysis Set

The full analysis set (FAS) is defined as all randomised patients who received at least one dose of study treatment and who have analysable data for at least one efficacy endpoint.

In practice, “analysable” is considered to mean an observed baseline and an observed post-baseline value for at least one efficacy endpoint.

The FAS will be used for presentation of demographic/baseline data and for summaries and analysis of efficacy.

Treatment assignment will be as randomised (i.e. planned maintenance treatment), but certain analyses will also consider assignment according to actual maintenance treatment (see [Section 6.1.3](#)).

Pharmacokinetic Set

The pharmacokinetic set (PKS) is defined as all patients in the TS who provide at least one evaluable BI 456906 plasma concentration which was not flagged for exclusion.

The table below summarises the analysis sets and their main intended purpose (specific details on sensitivity analyses, missing data, etc. are included in the relevant analysis section):

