7.5.2 Secondary endpoint(s)

No MCPMod dose finding analyses or subgroup analyses will be performed for secondary endpoints.

Responder secondary endpoints

The analysis of responder secondary endpoints will be performed on the FAS, using planned maintenance treatment, and including all data censored for COVID-19 related early treatment discontinuation.

A frequency table will be presented of those patients achieving percentage change from baseline in body weight at each time point (up to and including Week 46) of $\leq -5\%$, $\leq -10\%$, $\leq -15\%$ and $\leq -20\%$, respectively.

The analysis of responder secondary endpoints (which are defined only at Week 46) will be aligned with the estimand strategy specified in [Section 7.4.1](#) for the primary analysis. This will be done using a multiple imputation approach on the underlying continuous body weight values, as specified below. Missing body weight measurements will be imputed using actual values of body weight, not changes from baseline. The same random seed will be used as specified for the multiple imputation sensitivity analysis of the primary endpoint in [Section 7.4.2](#).

As the first step, non-monotone (intermediate) missing values will be imputed using the MCMC method. The details of the MCMC imputation step are exactly the same as those given in [Section 7.4.2](#).

Next, the remaining monotone missing values at each week will be imputed using the sequential regression method on each of the 1000 partially imputed datasets above. The imputations will be performed using the MAR assumption, which assumes that a patient with a missing value follows a similar trajectory to a similar patient without missing data in the same treatment group (where “similar patient” means with regard to both baseline covariates and non-missing values). The order in which the imputation model is specified is important for this step, and will be as follows: treatment, gender, baseline body weight, body weight at each scheduled post-baseline week in numeric week order.

Percentage change in body weight from baseline will then be derived for each patient in each of the 1000 completely imputed datasets, and from this each of the 3 responder definitions will also be derived for each patient. In other words, the multiple imputation steps will only be performed once for all relevant responder endpoints.

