7.8 SAFETY ANALYSIS

All safety analyses will be performed on the TS, using actual maintenance treatment, and including only on-treatment data (unless otherwise specified in [Section 7.8.1](#)), regardless of whether early treatment discontinuation was COVID-19 related.

Selected AE summaries will also be presented on the TS using planned maintenance treatment. Where this is also planned, it is clearly specified.

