7.8.1 Adverse Events

The analyses of adverse events will be descriptive in nature. All analyses of AEs will be based on the number of patients with AEs and not on the number of AEs.

The analysis of adverse events will be based on the concept of treatment emergent adverse events. AEs will be considered “on-treatment” if the AE start date meets the 28-day REP criterion (see [Section 6.1.6](#)). AEs occurring prior to the start of treatment will be assigned to “screening”. AEs occurring more than 28 days after the last dose of study treatment will be assigned to “follow-up”. Unless otherwise specified, on-treatment AEs will be pooled across dose escalation and maintenance periods. It should also be noted that the protocol encourages continued study participation for patients who have discontinued treatment early. It is therefore expected that for some patients there will be off-treatment data captured during the planned treatment period, which will make the “follow-up” period included in AE summaries longer than the 4-week definition of scheduled “follow-up” used in the protocol, perhaps in some cases considerably longer than this.

An overall summary of adverse events will be presented for all treated patients. This summary will show the number and percent of patients with any AE, any investigator defined drug-related AE, any AE leading to the discontinuation of study medication, any AESI (as determined by the investigator), any serious AE (including reason for serious (death, life-threatening, disability/permanent damage, required or prolonged hospitalization, congenital anomaly/birth defect and other medically important events)), and any drug-related serious AE. The overall summary will be presented:

- Using actual maintenance treatment, with the treatment period pooled across, and split into, dose escalation and maintenance periods, respectively.
- Using planned maintenance treatment, with the treatment period pooled across dose escalation and maintenance periods only.

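### Maintenance-period AE percentages count patients who never entered maintenance, and do so unequally across the dose columns

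*SAP*

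**What the plan says.** - **Set.** SAP 6.3: "The treated set (TS) is defined as all randomised patients who received at least one dose of study treatment". Reaching maintenance is not required, and no set of maintenance entrants is defined.
- **Columns.** SAP 7.8: "All safety analyses will be performed on the TS, using actual maintenance treatment, and including only on-treatment data".
- **Split.** SAP 7.8.1 presents the overall AE summary "Using actual maintenance treatment, with the treatment period pooled across, and split into, dose escalation and maintenance periods, respectively", and uses the same wording for all AEs by SOC and PT. The versions by planned treatment are pooled over both periods only.
- **Denominator.** SAP 7.8.1 states none for the split tables. The general rule for categorical tabulations in SAP 7 is: "Percentages will be based on all patients in the respective patient set whether they have non-missing values or not".
- **Patients who stop in escalation.** SAP 6.1.3: "actual maintenance treatment will be defined as the next planned maintenance dose up from the last dose which was taken prior" to the dose at discontinuation. Table 6.1.3:1 sends stops at 0.3 or 0.6 mg to the 0.6 mg column, 0.9 to 2.4 mg to 2.4 mg, 3.0 to 4.2 mg to 3.6 mg, and 4.8 mg to 4.8 mg. For placebo: "All patients randomised to placebo maintenance treatment will be assigned to placebo for actual maintenance treatment".

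**The concern.** A patient who stopped in week 6 cannot have an AE on maintenance treatment, yet under the general rule that patient lowers the maintenance AE percentage of some column. This would understate incidence even by randomised arm. By actual treatment there is a second problem: Table 6.1.3:1 gives each such patient a maintenance dose that was never taken in maintenance, and the columns do not receive these patients in equal shares. The understatement then differs between doses.

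The maintenance half of these tables is the direct display of tolerability at a stable dose. The protocol's primary objective includes defining a dose range on safety and tolerability, and SAP 7.4.1 says that tolerability and safety will weigh in the Phase 3 dose choice. A pattern across columns that comes from the denominators could be read as a property of the dose.

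**Working it through.** The plan gives no figure on this point, so there is none to reproduce. As a check on the column rule, applying its wording (lowest planned maintenance dose above the previous dose) reproduces all 11 rows of Table 6.1.3:1.

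**A result that needs no stopping rate.** In Protocol Table 4.1.4:1 the highest dose in any arm during weeks 1-10 is 1.8 mg. Every dose up to 1.8 mg maps to the 0.6 or 2.4 mg column. So no stop in weeks 1-10 enters the 3.6 or 4.8 mg denominator, whatever the arm.

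**Inputs for the size.** From the documents: 70 per arm, ten two-week escalation steps per arm, and the column mapping. Assumed: stopping rates and timing, and a true maintenance AE risk of 50% in every column, so that any gradient is an artefact. Step-downs are ignored unless stated, and third-week holds throughout.

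Number of escalation steps that map to each column:

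| Arm | 0.6 | 2.4 | 3.6 | 4.8 |
|---|---|---|---|---|
| A (0.6 mg) | 10 | 0 | 0 | 0 |
| B (2.4 mg) | 2 | 8 | 0 | 0 |
| C (3.6 mg) | 2 | 5 | 3 | 0 |
| D (4.8 mg) | 2 | 4 | 2 | 2 |
| Total | 16 | 17 | 5 | 2 |

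**Formula.** Shown % = 50 × entrants / (entrants + stoppers assigned to the column). For placebo it is 50 × (1 − stopping rate).

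**Worked case: 20% stop in each arm, evenly over weeks 1-20.** Stoppers per arm are 14, or 1.4 per step; entrants are 56 per column.

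- 0.6 mg: 16 × 1.4 = 22.4 stoppers; 56/78.4 = 71.4%; shown 35.7
- 2.4 mg: 17 × 1.4 = 23.8; 56/79.8 = 70.2%; shown 35.1
- 3.6 mg: 5 × 1.4 = 7.0; 56/63.0 = 88.9%; shown 44.4
- 4.8 mg: 2 × 1.4 = 2.8; 56/58.8 = 95.2%; shown 47.6

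**Other scenarios (true value 50 in every column).** Dose-related means 5% on placebo and 5/15/20/30% in arms A to D.

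| Stopping in escalation | Placebo | 0.6 | 2.4 | 3.6 | 4.8 |
|---|---|---|---|---|---|
| 5% per arm, even | 47.5 | 46.1 | 45.9 | 48.7 | 49.5 |
| 10% per arm, even | 45.0 | 42.5 | 42.1 | 47.4 | 48.9 |
| 20% per arm, even | 40.0 | 35.7 | 35.1 | 44.4 | 47.6 |
| 30% per arm, even | 35.0 | 29.7 | 28.9 | 41.2 | 46.1 |
| Dose-related, even | 47.5 | 42.0 | 35.7 | 43.5 | 46.1 |
| Same, plus step-down of 10/10/20% in B/C/D | 47.5 | 43.1 | 34.6 | 43.9 | 45.2 |
| Dose-related, none before week 5 | 47.5 | 47.5 | 33.3 | 42.1 | 45.2 |
| Dose-related, all in weeks 17-20 | 47.5 | 47.5 | 42.5 | 40.0 | 35.0 |

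With equal, even stopping, the false rise from 2.4 to 4.8 mg is 49.5 − 45.9 = 3.6 points at 5% and 46.1 − 28.9 = 17.2 points at 30%. In the last row the pattern is a false fall of 47.5 − 35.0 = 12.5 points from 0.6 to 4.8 mg.

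**With entrants as the denominator,** every column shows 50 in every scenario. In the worked case the active-column denominators change from 78.4/79.8/63.0/58.8 to 56 each.

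**The case against.** **The denominator is inferred.** The quoted sentence is a general rule whose wording is aimed at missing values, and SAP 7.8.1 gives no N for the split tables. The protocol adds that safety summaries follow sponsor standards, which are not in the documents. This stands as a caution. But no exception is written, so a programmer who follows the SAP would use all treated patients.

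**Other displays exist.** SAP 7.8.1 plans an exposure-adjusted table with its own time at risk, and SAP 7 plans disposition counts by period and Kaplan-Meier curves of discontinuation. None replaces the missing percentages: the exposure-adjusted table is not split by period, and the disposition counts use planned treatment, so they do not give N for the actual-treatment columns.

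**The direction is not fixed.** A reader might infer that the low-dose columns are always diluted most, or that the plan builds a rising dose gradient into safety as a whole. The documents support neither:

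- Timing decides the sign. Without stops before week 5, 0.6 mg equals placebo and only 2.4 mg is strongly low; late dose-related stopping dilutes 4.8 mg most.
- The pattern is often not monotone once placebo is included.
- Step-down matters too: under Protocol 4.1.4, "Patients of Group C and B will then follow scheme of group A", which adds maintenance entrants to the 0.6 mg column.
- Only the maintenance half of two descriptive tables is affected. The pooled, planned-treatment, serious, drug-related and discontinuation tables do not use this denominator.

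**By-visit responder table.** One might extend the point to SAP 7.5.2: "A frequency table will be presented of those patients achieving percentage change from baseline in body weight at each time point". That does not follow. An all-FAS denominator counts a missing weight as non-response, which is a defensible conservative display. Weights after treatment stop are used except after COVID-19-related stops, and the Week 46 analysis uses multiple imputation. A denominator of observed values would bring its own selection.

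**Conclusion.** The point holds for the maintenance halves of the overall AE summary and the SOC/PT table by actual treatment. The SAP's own rules, followed literally, put patients who were never at risk into those denominators, and Table 6.1.3:1 distributes them unequally over the dose columns. That every active-arm stop in weeks 1-10 goes to 0.6 or 2.4 mg follows from the documents alone.

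The size does not. It rests on assumed stopping rates and timing and an assumed 50% risk: about 4 to 17 points of false rise from 2.4 to 4.8 mg with equal, even stopping of 5-30%, and a false fall with late dose-related stopping. The sound conclusion is that these percentages are not comparable across doses, not that they are biased in a known direction. The tables are descriptive and no test depends on them, but no other planned table shows incidence by dose in maintenance, so the change should be made.

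**What to change.** In SAP 7.8.1, state for the maintenance-period half of both tables:

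- N and % are based on Treated Set patients who took at least one dose on or after Visit 12, by actual maintenance treatment, with this N in the column header.
- AEs in the 28 days after an escalation-phase stop are counted in the escalation period, so that numerator and denominator refer to the same patients.
- All-treated denominators are kept for the pooled and escalation tables.

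The cost is one passage of SAP wording and one derived flag, with no new data. There is a small downside: the maintenance percentages then describe only patients who tolerated escalation. A footnote should say so, and the table should be read beside the escalation and pooled tables.

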7.1 DEMOGRAPHIC AND OTHER BASELINE CHARACTERISTICS

Descriptive summaries of demographic variables and characteristics measured at baseline will be presented, to include: sex, race and ethnicity, age (years) (continuous and categories), height (cm), weight (kg) (continuous and categories), BMI (kg/m²) (continuous and categories), waist circumference (cm), systolic BP (mmHg), diastolic BP (mmHg), pulse rate (bpm), country and region.

Age, body weight and BMI categories will be as defined in [Section 6.4](#).

Summaries of demographic data and baseline characteristics will be presented on both the FAS using planned maintenance treatment and the TS using actual maintenance treatment.

